## APPENDIX VII: COGNITIVE TESTING

### Neurocognitive Testing

Symbol Digit Modalities Test - copyright©

## KEY

(	-	+	Γ	+	>	+	)	÷
1	2	3	4	5	6	7	8	9

С Т - С Т > - Г С > - С > 67

Γ > C ÷ T > T Γ C ÷ > ÷ T C

Γ + + ) ( + Γ ) ÷ +

÷ Γ ⊖ ( > Γ ( ⊖ + ÷ ) ⊕ > Γ

÷ + ) ) T > + - + ÷ ÷ ) (

> ÷ + - × > Γ ÷ ( + ÷ - ⊥ > ) Γ

÷ Q + ÷ T + ) T ( ÷ ÷ ( Γ T >

[figure not shown]
– ÷ ( > Γ ÷ ( > ÷ + T – Γ ) ÷

[figure not shown]
NCI Version Date: 9/24/2018

## Update #7

## Trail Making

[figure not shown]
### Part A

[figure not shown]

**FOR  
PRACTICE  
USE  
ONLY**

**TRAIL MAKING  
PART B  
SAMPLE**

**APPENDIX VIII: ADMINISTRATION PROCEDURES FOR THE NEUROCOGNITIVE TEST BATTERY**

**ADMINISTRATION PROCEDURES FOR THE NEUROCOGNITIVE TEST BATTERY**

**Please note: All personnel who administer the cognitive testing will need to be certified.  
Please see section 4.1**

1. **Testing should be completed in one session. Test instructions must be followed verbatim with every patient at every study visit. All tests should be completed in black pen.**

**PLEASE NOTE: If a patient is unable to complete the test due to cognitive deterioration, it is best to attempt the test and proceed until the patient meets discontinuation criteria. Then mark down at the bottom of each test form “Discontinued” and fill in the reason (e.g. could not understand the instructions). This is much preferred to not completing the test at all and should not be frustrating to the patient as it will only take a few minutes of the patient’s time.**

2. **Originals of the test booklets should be mailed to**

3. **Please keep copies of all original test booklets. In the event of questions, contact the RPS III or QAS of the study (contact information can be found in the protocol on the Resource page).**
4. **Patients should not be given copies of their tests to avoid learning the material between test administrations.**

**Setting up for Neuropsychological Testing**

**Set up of testing situation:**

- Private room**
- Door that closes**
- Quiet**
- Alone with just the patient-- No family members**
- May want to hang a sign that says “do not disturb”**
- Some tests are timed – it is very important not to be interrupted**
- Desk for you both to write on (clipboard works in a pinch)**
- Stopwatch**
- Black ink pens (one for you and one for the patient)**

**Testing tips**

- Do not indicate to the patient how well they are doing**
- Hide your writing from the patient so they cannot get feedback on how they are performing**
- However, it is OK to be generically encouraging (make sure you make the same response whether patient is performing well or not)**
- Please do not assist them in any way if they struggle with a task; we need an accurate view of what they can do themselves.**

**TEST INSTRUCTIONS**

**Administer the tests in the following order to every patient at every visit**

**1. Symbol Digit Modalities Test (Smith, 1982)**

The SDMT requires the subject to insert a numbers matching to geometric figures presented in random order. The appropriate number is shown in a key containing the Arabic numerals 1 through 9, each of which is paired with a different geometric symbol. To administer the test, place the form in front of the examinee. Read the instructions verbatim. These are taken directly from the test manual (Smith, 1982) and read as follows:

*"Please look at these boxes at the top of the page. You can see that each box in the upper row has a little mark in it. Now look at the boxes in the row just underneath the marks. Each of the boxes under the marks has a number. Each of the marks in the top row is different, and under each mark in the bottom row is a different number.*

*Now look at the next line of boxes (examiner points to the line of boxes) just under the top two rows. Notice that the boxes on the top have marks, but the boxes underneath are empty. You are to fill each empty box with the number that should go there according to the way they are paired in the key at the top of the page. For example, if you look at the first mark, and then look up at the key, you will see that the number 1 goes in the first empty box. So write the number 1 in the first box. Now, what number should you put in the second box? (Number 5) That's right. So write the number 5 in the second box. What number goes in the third box? (Number 2) Two, right. That is the idea. You are to fill in each of the empty boxes with the numbers that should go in them according to the key. Now for practice, fill in the rest of the boxes until you come to the double line. When you come to the double line, stop."*

**The examiner should check to see that each examinee understand the task. Any errors made in the first 10 practice responses (before the double line) should be immediately pointed out by the examiner and corrected by the examinee. If an examinee has not understood the nature of the task, the instructions are repeated with further examples until the nature of the test is clearly understood. The examinee then continues with the following instructions.**

“You will have a minute for each letter. The first letter is ‘\_\_\_’ (see scoring sheet).

\*\*Allow exactly one minute for each letter\*\*

- If the patient discontinues before the end of the time period, encourage him/her to try to think of more words.
- If he/she is silent for 15 seconds, repeat the basic instruction and the letter (e.g., “Tell me all the words you can think of that begin with a “c”).
- No extension on the time limit is made in the event that instructions are repeated.
- Continue the evaluation with the remaining two letters, allowing one minute for each.

**Recording and Scoring:**

- The COWA provides lines on which the patient’s responses can be entered (e.g., write in the word that is said by the patient). If his/her speed of word production is too fast to permit verbatim recording, a “+” should be entered to indicate a correct response.
- Incorrect responses either should not be recorded or, if recorded, should be struck through with a line.
- If the patient provides more responses than there are lines on the record sheet, place check marks in the boxes to indicate correct responses only.
- Count all the correct responses. The number of correct words should be indicated below each column.

**Comments on scoring:**

- Note: It can be helpful for the first several patients and for patients known to be fast with their word production to tape record the session for transcription at a later time.
- The instructions include a specific prohibition against giving proper names or different forms of the same word. Therefore, inflections of the same word (e.g., eat-eating; mouse-mice; loose-loosely; ran-run-runs) are not considered correct responses.
- Patients often give both a verb and a word derived from the verb or adjective (e.g., fun-funny; sad-sadness). These are not considered correct responses. On the other hand, if the word refers to a specific object (e.g., foot-footstool; hang-hanger), it would be counted as a correct answer.
- Many words have two or more meanings (e.g., foot; can; catch; hand). A repetition of the word is acceptable IF the patient definitely indicates the alternative meaning to you.
- Slang terms are OK if they are in general use.
- Foreign words (for example, pasta; passé; lasagna) can be counted as correct if they can be considered part of the lexicon of the relevant language, the criterion being their listing in a standard dictionary of that language. All incorrect and repeated responses MUST be crossed out with one single line, initialed and dated. Additionally, all duplicate entries that have been verified to have different meanings must be marked “ok”, initialed and dated. Refer to the descriptions above for guidelines for acceptability. Add the total number of correct responses in each column and input the totals where indicated on the COWA worksheet.
- If the test is discontinued or omitted, please mark this on the bottom of the test form.

**3. TRAIL MAKING TEST [Timed Test]**

Page 4 of 7

**Instructions are included verbatim in the test booklet**

NCI Version Date: 9/24/2018

Update #7

**Part A – Sample:**

The Sample for Part A must be completed/attempted by each patient at every assessment. Place the Sample A worksheet flat on the table, directly in front of the patient (the bottom of the worksheet should be approximately six inches from the edge of the table). Give the patient a black pen and say:

Examiner: “On this page (point) are some numbers. Begin at number 1 (point to 1) and draw a line from 1 to 2 (point to 2), 2 to 3 (point to 3), 3 to 4 (point to 4), and so on, in order, until you reach the end (point to the circle marked END). Draw the lines as fast as you can. Ready, begin.”

If the patient completes Sample A correctly and in a manner demonstrating that s/he understands what to do, proceed immediately to Test A. If the patient makes a mistake on Sample A, point out the error and explain it.

The following explanations of mistakes serve as illustrations:

- “This is where you start (point to number 1)”
- “You skipped this circle (point to the circle omitted)”
- “You should go from number 1 to 2, 2 to 3, and so on, until you reach the circle marked END”

If it is clear that the patient intended to touch a circle but missed it, do not count it as an omission. Remind the patient, however, to be sure to touch the circles. If the patient still cannot complete Sample A, take his/her hand and guide him/her through the trail using the opposite end of the pen, lightly touching the worksheet to avoid making marks on the copy. Then say:

Examiner: “Remember, begin at number 1 (point to 1) and draw a line from 1 to 2 (point to 2), 2 to 3 (point to 3), 3 to 4 (point to 4) and so on, in order, until you reach the circle marked END (point). Do not skip around, but go from one number to the next in proper order. Remember to work as fast as you can. Ready, begin.”

If the patient does not succeed, or it becomes evident that s/he cannot do the task, DISCONTINUE testing and indicate the corresponding reason on the Trail Making A & B Scoring (TMABS) sheet. If the patient completes Sample A correctly and appears to understand what to do, proceed immediately to Part A.

**Part A – Test:**

After the patient has completed Sample A, place the Part A test worksheet directly in front of the patient and say:

Examiner: “Good! Let’s try the next one. On this page are numbers from 1 to 25. Do this the same way. Begin at number 1 (point) and draw a line from 1 to 2 (point to 2), 2 to 3 (point to 3), 3 to 4 (point to 4) and so on, in order, until you reach the circle marked END (point). Do not skip around, but go from one number to the next in proper order. Remember to work as fast as you can. Ready, begin.”

- Start timing as soon as the instruction is given to “begin.”
- Watch closely in order to catch any errors as soon as they are made. If the patient makes an error, call it to his/her attention immediately and have him/her proceed from the point the mistake occurred (In other words, have them go back to the last correct circle).
- The patient must complete the test in 3 minutes or less
- DO NOT STOP TIMING UNTIL HE/SHE REACHES THE CIRCLE MARKED “END.”
- If the patient does not complete the test within 3 minutes terminate the testing. The test can also be discontinued if the patient is extremely confused and is unable to perform the task. Complete the Trail Making A & B Scoring (TMABS) sheet indicating the reason the test was terminated and the last correct number reached on the test.
- If the patient successfully completes the test, record the time to completion on the Trail Making A & B Scoring (TMABS) sheet in minutes and seconds. Then say, “That’s fine. Now we’ll try another one.”

**Part B – Sample:**

The Sample for Part B must be completed/attempted by each patient at every assessment. Place the Sample B worksheet flat on the table, directly in front of the patient (the bottom of the worksheet should be approximately six inches from the edge of the table) and say: Examiner: “On this page (point) are some numbers and letters. Begin at number 1 (point to 1) and draw a line from 1 to A (point), A to 2 (point to 2), 2 to B (point to B), B to 3 (point to 3), 3 to C (point to C) and so on, in order, until you reach the end (point to the circle marked END). Remember, first you have a number (point to 1), then a letter (point to A), then a number (point to 2), then a letter (point to B), and so on. Draw the lines as fast as you can. Ready, begin.”

If the patient completes Sample B correctly, and in a manner demonstrating that s/he understands what to do, proceed immediately to Part B. If the patient makes a mistake on Sample B, point out the error and explain it.

The following explanations of mistakes serve as illustrations:

- “You started with the wrong circle. This is where you start (point to number 1)”
- “You skipped this circle (point to the circle omitted)”
- “You should go from number 1 (point) to A (point), A to 2 (point to 2), 2 to B (point to B), B to 3 (point to 3) and so on, until you reach the circle marked END (point)”

If it is clear the patient intended to touch a circle but missed it, do not count it as an omission. Remind the patient, however, to be sure to touch the circles. If the patient still cannot complete Sample B, take their hand and guide them through the trail using the opposite end of the pen, lightly touching the worksheet to avoid making marks on the copy. Then say:

Examiner: “Now you try it. Remember, begin at number 1 (point to 1) and draw a line from 1 to A (point to A), A to 2 (point to 2), 2 to B (point to B), B to 3 (point to 3) and so on, in order, until you reach the circle marked END (point). Ready, begin.”

If the patient does not succeed or it becomes evident that s/he cannot do the task, DISCONTINUE testing and indicate the corresponding reason on the Trail Making A & B Scoring (TMABS) sheet. If the patient completes Sample B correctly and appears to understand what to do, proceed immediately to Part B.

Page 6 of 7

**Part B – Test:**

After the patient has completed Sample B, place the Part B Worksheet directly in front of the patient and say:

Examiner: "Good! Let's try the next one. On this page are both numbers and letters. Do this the same way. Begin at number 1 (point) and draw a line from 1 to A (point to A), A to 2 (point to 2), 2 to B (point to B), B to 3 (point to 3), 3 to C (point to C) and so on, in order, until you reach the circle marked END (point). Remember, first you have a number (point to 1), then a letter (point to A), then a number (point to 2), then a letter (point to B), and so on. Do not skip around, but go from one circle to the next in the proper order. Draw the lines as fast as you can. Ready, begin."

- Start timing as soon as the instruction is given to "begin."
- Watch closely in order to catch any errors as soon as they are made. If the patient makes an error, call it to his/her attention immediately and have him/her proceed from the point the mistake occurred (In other words, have them go back to the last correct circle).
- The patient must complete the test in 5 minutes or less.
- DO NOT STOP TIMING UNTIL HE/SHE REACHES THE CIRCLE MARKED "END."
- Record the time to completion on the Trail Making A & B Scoring (TMABS) in minutes and seconds.
- If the patient does not complete the test within 5 minutes terminate the testing. The test can also be discontinued if the patient is extremely confused and is unable to perform the task. Complete the Trail Making A & B Scoring (TMABS) sheet indicating the reason the test was terminated and the last correct number or letter reached on the test.
- If the patient successfully completes the test, record the time to completion on the Trail Making A & B Scoring (TMABS) sheet in minutes and seconds.

**APPENDIX IX: NEUROCOGNITIVE EVALUATIONS SUBMISSION FAX FORM**

**Neurocognitive Evaluations Submission Fax Form**

Fax completed form to:

[REDACTED]

From: \_\_\_\_\_

Date: \_\_\_\_\_

Re: Neurocognitive Evaluations Booklet Submission

Attention: A completed Neurocognitive Evaluations booklets (completed Patient and Examiner Questionnaire Booklets) have been sent to you via surface mail, as of \_\_\_\_\_ (date).

Contact Information: \_\_\_\_\_

Person administering test: \_\_\_\_\_

Name of site: \_\_\_\_\_

Phone: \_\_\_\_\_

Email: \_\_\_\_\_

Patient's study ID #: \_\_\_\_\_

## APPENDIX X: BAYES SHADOW STATISTICAL DESIGN

### Bayes Shadow Statistical Design

The primary endpoint for the trial is the response rate in terms of a clinically meaningful improvement in patient-reported fatigue, defined as at least a two-point improvement in fatigue as measured by the worst fatigue item from the Brief Fatigue Inventory at 8 weeks, and the design proposed for this study will randomize a minimum of 30 evaluable patients and a maximum of 120 evaluable patients to one of three treatment arms. The Bayesian adaptive randomization design (98) will work as follows. The first 30 patients will be randomized in a 1:1:1 fashion to the three treatment arms (block size of 30 will be used to guarantee an equal number of patients are randomized to each treatment arm). After the 30th patient has been randomized, the adaptive randomization procedure will begin. As a shadow design, we will use the data from the completed Fisherian design and then assess the different assignations that would have been made via the Bayes design and its impact on the trial results.

Adaptive randomization: We assume that the fatigue response outcome, denoted  $X_{i,j}$ , of patient  $i$  on treatment  $j$  derives from a  $\text{Binomial}(\pi_j)$  distribution ( $j=1$  for placebo;  $j=2$  for armodafinil 150 mg). We assume that  $\pi_j$  derives from a Beta  $(\alpha_j, \beta_j)$  distribution. Given limited historical data, we use a uniform non-informative prior for each arm ( $\alpha_1=\alpha_2=1$ ;  $\beta_1=\beta_2=1$ ). We repeat this calculation for the comparison of the placebo versus the armodafinil 250 mg arm and normalize the result to get three probabilities for treatment assignation.

As each patient is enrolled, the randomization probability for each treatment arm is recomputed using all currently available fatigue response data from already accrued patients. The randomization procedure computes the posterior probability for each treatment of being the best between the two treatments (where  $p_j$  = probability that treatment  $j$  is better than the other treatment) and assigns the patient to arm  $j$  with probability  $p_j$  (i.e.,  $\lambda=1$  in the notation of Cook [100]). This procedure uses all observed fatigue response data at the time of the patient's randomization to unbalance the randomization probabilities in favor of the treatment arm having comparatively superior symptom response outcomes.

Efficacy stopping rules: If at any time prior to full accrual the probability that an arm is superior to the other arm given all available data falls below 0.05 ( $P_L$  in the notation of the Adaptive Randomization software used below), that arm is suspended (though it potentially could reopen should the results on the other arm substantially worsen). If at any time prior to full accrual the probability that an arm is superior to the other arm given all available data rises above 0.95 ( $P_U$  in the notation of the Adaptive Randomization software used below), that arm is declared the winner and the trial is stopped early.

Decision rule: If the trial runs through completion without early stopping and if the largest probability for the two armodafinil treatment arms is better than that for the placebo arm is greater than 0.80 ( $P_U^*$  in the notation of the Adaptive Randomization software used below), then that treatment is declared the winner of the trial.

Operating characteristics: Operating characteristics of a clinical trial with the above parameters and accrual rate were simulated (10,000 replicates) using software developed by the M. D. Anderson Cancer Center Department of Biostatistics (available at:<http://biostatistics.mdanderson.org/SoftwareDownload/>):

Arm 	True Confirmed Fatigue Response Rate	Pr(Selected) 	Pr(Selected Early) 	Pr(Stopped Early) 	Average Number of Evaluable Patients Treated	Average Trial Duration
1	10%	0.20	0.07	0.07	34	27.6 mo
2	10%	0.20	0.07	0.07	34	
1	10%	0.09	0.04	0.21	29	26 mo
2	15%	0.41	0.19	0.04	36	
1	10%	0.03	0.02	0.39	24	23.5 mo
2	20%	0.63	0.36	0.02	35	
1	10%	0.02	0.01	0.57	20	20.4 mo
2	25%	0.80	0.54	0.01	33	
1	10%	<0.01	<0.01	0.73	18	17.4 mo
2	30%	0.90	0.69	<0.01	29	

1. 1=placebo, 2=best of armodafinil arms.
2. The overall probability that the given arm is selected as being the best treatment after the trial has ended.
3. The probability that the given arm is selected as being the best treatment arm early (prior to all patients being enrolled).
4. The probability that the given arm is dropped for any reason (due to futility or another arm being selected).

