## 16.0 STATISTICAL CONSIDERATIONS AND METHODOLOGY

### 16.1 Study Design

This is a three-arm randomized clinical trial. The primary goal of this study is to compare the response rate of patients randomized to one of two doses of armodafinil or placebo in terms of a clinically meaningful improvement in patient-reported fatigue of at least a two-point improvement in the 0-10 point Brief Fatigue Inventory usual fatigue item at eight weeks post-treatment initiation. Endpoints will be assessed per arm and compared across arms by comparing each armodafinil arm versus the placebo arm in turn. We make no adjustment for multiple comparisons as we want to err on the side of moving forward the appropriate dose into phase III testing upon the basis of promising information in the proposed trial.

The three arm randomized trial will accrue a maximum of 330 patients to randomize a 100 evaluable patients per arm based on a binary endpoint to armodafinil or placebo.

Bayesian adaptive “shadow” design: Bayes clinical trial designs are becomingly increasingly more popular as alternatives to classic Fisherian designs, especially in the phase I context (110). They have not, however, been applied to cancer control cooperative group clinical trials. As a feasibility exercise, we will use the results of this trial to “shadow” what would have happened if the Bayes design would have been used. This will provide us insights into the relative utility of the Bayes design within the context of cooperative group cancer control clinical trials. The potential advantage of the Bayes approach is that the study likelihood of efficacy is constantly monitored allowing for the possibility of early study completion and therefore a smaller number of patients put at risk (see MD Anderson Cancer Center Technical Report UTMDABTR-002-06 (98). There are a number of logistical and statistical issues that were raised in the review of the concept (which initially proposed a Bayes design) that we decided it would be more prudent to use a classic Fisherian design to run the trial and use a shadow design to obtain preliminary data for planning future cancer control clinical trials using a Bayes approach. The details for the Bayes design are attached as Appendix X.

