### 16.3 Primary Endpoint

The primary endpoint of this trial is the response rate in terms of a clinically meaningful improvement in patient-reported fatigue at 8 weeks. A response is defined as an improvement of 2 points on the 0-10 scale of the usual fatigue on the BFI.

All patients meeting the eligibility criteria who have signed a consent form, have begun treatment, and have not had a major treatment violation within the 1st cycle of treatment will be evaluable for the primary endpoint. Patients will be analyzed according to the arm in which they were randomized.

Comparison of the primary endpoint between arms will be based on a binomial point estimate computed for each arm and a Fisher's exact test will be the inferential hypothesis test.

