## 16.4 Secondary Endpoints

**16.4.1 Other time points:** The same analyses carried out using the 8 week assessment data will be used for analysis of data from the other time point assessments.

**16.4.2 Other fatigue measures:** The other fatigue items ("usual", "usual" and "now") as well as the impact of fatigue items from the BFI, the PRO-CTCAE, and the summated score from the PROMIS fatigue measure will be analyzed separately in turn comparing the average of these variables for each treatment using Kruskal-Wallis testing for change from baseline to four weeks, AUC over the entire treatment period, and repeated measures ANOVA using all treatments and all time points.

**16.4.3 Cognitive function:** The same analyses outlined for the other fatigue measures will be carried out for each of the cognitive function tests.

**16.4.4 Quality of life:** The same analytical approaches will be used to compare the three treatments in terms of QOL as was outlined for the other fatigue measures.

**16.4.5 Safety and tolerability of armodafinil:** Comparison of the proportion of patients reporting adverse events via the CTCAE items will be compared across treatment arms using a Fisher's exact test.

**16.4.6 Area under the curve (AUC) and summary statistics:** For the continuous measures mentioned above, AUC summary statistics will be generated for each patient to represent the overall experience reported by patients for each endpoint (e.g. fatigue) by combining the data from baseline, weeks 4, and 8 assessment points. The average of these AUC variables will be compared between the two treatment arms using two-sample t-tests. Further summary statistics will be constructed for the categorical variables to indicate whether the patient ever responded over the entire treatment period. These categorical variables will be compared between treatment groups via Fisher's exact tests.

**16.4.7 Repeated measures analysis:** The overall experimental layout will be examined via the construction of a repeated measures model using data from all assessment time points involving the continuous variables described above. Tests for time by treatment interaction will be carried out by the profile analysis methods of Srivastava. Covariates such as age, gender and other clinical variables may be included to test their impact on the initial efficacy tests of the primary and secondary analyses described above. Use of the Optune® device will also be included as a descriptive factor.

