## 16.5 Statistical Design

The primary endpoint for the trial is the response rate in terms of a clinically meaningful improvement in patient-reported fatigue, defined as at least a two-point improvement in fatigue as measured by the usual fatigue item from the Brief Fatigue Inventory at 8 weeks. This change

will be from baseline to 8 weeks (after randomization). The design proposed for this study will randomize a maximum of 330 evaluable patients to one of three treatment arms.

**Efficacy stopping rules:** This study will be monitored by Alliance Data and Safety Monitoring Board (DSMB) every 6 months for safety and efficacy. If at any time prior to full accrual the p-value for the Fisher's exact test that an arm is superior to the other arm given all available data falls below 0.001 then consideration will be given to stopping the trial early.

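### Appendix X puts the primary endpoint on the worst-fatigue item while Section 16 uses the usual-fatigue item; followed as written, the Bayes shadow would be scored on different responders

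*Combined protocol and SAP*

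**What the plan says.** Section 16 defines response on the BFI usual-fatigue item three times:

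- Section 16.1: at least a "two-point improvement in the 0-10 point Brief Fatigue Inventory usual fatigue item at eight weeks post-treatment initiation".
- Section 16.3: "A response is defined as an improvement of 2 points on the 0-10 scale of the usual fatigue on the BFI".
- Section 16.5: improvement "as measured by the usual fatigue item from the Brief Fatigue Inventory at 8 weeks".

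Appendix X opens with a sentence almost identical to the one in Section 16.5, also presented as the primary endpoint of the trial, but there the improvement is "as measured by the worst fatigue item from the Brief Fatigue Inventory at 8 weeks". Appendix III shows that usual and worst are separate questions (BFI questions 2 and 3). Section 2.1 names the BFI at 8 weeks without an item, so it does not settle the matter.

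The purpose of the shadow is in Section 16.1: "we will use the results of this trial to “shadow” what would have happened if the Bayes design would have been used". The expected return is also stated there: "This will provide us insights into the relative utility of the Bayes design within the context of cooperative group cancer control clinical trials". Appendix X adds that the completed trial's data will be used to examine the assignments the Bayes design would have made and their effect on the results.

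Section 16.4.2 begins its list of secondary measures with "The other fatigue items ('usual', 'usual' and 'now". The primary item is therefore listed twice and worst is not named.

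**The concern.** A shadow analysis isolates the effect of the design only if both designs score the same patients as responders. Under Appendix X as written, the adaptive assignment probabilities, arm suspension, early stopping and the declared winner would all be driven by worst-item responders. The Fisher test in Section 16.3 would be driven by usual-item responders. If the two analyses then disagreed, the reader could not tell how much was due to the Bayes rules and how much to the item.

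Appendix X does not present the worst item as a separate endpoint for the shadow. It restates the trial's own primary endpoint with a different item. That is a contradiction between two parts of the plan, and it should be settled before the shadow analysis is run so that the item is not chosen after the data are seen.

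**Working it through.** **Inputs.** From the documents: 10% placebo and 25% active response (Section 16.2); uniform Beta(1,1) priors, assignment probability equal to the posterior probability of being better, thresholds 0.05 and 0.95 during accrual and 0.80 at the end (Appendix X). Assumed, because the documents give no value: correlation ρ of 0.6 to 0.9 between the changes on the two items, and equal response rates on both.

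**1. Reproduce the plan's own figures.** With s responders and f non-responders in an arm, the posterior is Beta(1+s, 1+f). The simplified version has two arms, 20 patients assigned alternately, then adaptive assignment to a maximum of 80, with outcomes known at once (1,500 runs).

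| True rates | Source | Pr(active selected) | Selected early | Mean n, placebo / active |
|---|---|---|---|---|
| 10% v 25% | Appendix X table | 0.80 | 0.54 | 20 / 33 |
| 10% v 25% | Simplified version | 0.81 | 0.55 | 20 / 35 |
| 10% v 10% | Appendix X table | 0.20 | 0.07 | 34 / 34 |
| 10% v 10% | Simplified version | 0.19 | 0.06 | 37 / 38 |

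This is close enough to use. A two-arm maximum of 120 gives 0.90 and 0.70 at 10% v 25%, which does not match the table.

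**2. How far the two items pick the same responders.** With bivariate-normal changes and response rate p on each item, the proportion responding on both is q = Φ₂(Φ⁻¹(p), Φ⁻¹(p); ρ). The share of worst-item responders who are also usual-item responders is q/p, and the proportion of patients classified differently is 2p − 2q.

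- p = 0.25, ρ = 0.7: q = 0.150; q/p = 0.60; 2(0.25) − 2(0.150) = 0.20.
- p = 0.25, ρ = 0.9: q = 0.193; q/p = 0.77; 2(0.25) − 2(0.193) = 0.11.
- Across ρ = 0.6, 0.7, 0.8, 0.9 at p = 0.25: q/p = 0.54, 0.60, 0.68, 0.77.

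**3. Effect on the shadow result.** Each simulated trial was put through the simplified rules once on each item, with a separate randomisation sequence for each. Each arm had its own fixed sequence of patients, as when completed data are replayed (6,000 runs; Monte Carlo standard error about √(0.25 × 0.75/6000) = 0.6 points). The last column reruns the same item with a new randomisation sequence only.

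| True rates, both items | Result differs between items, ρ = 0.6 / 0.7 / 0.8 / 0.9 | Opposite winners | Same item, new randomisation |
|---|---|---|---|
| 10% v 25% | 26 / 25 / 22 / 20% | 1.0-1.8% | 7-8% |
| 10% v 10% | 51 / 48 / 45 / 40% | 2.5-5.0% | 13-14% |
| 10% v 30% | 13 / 13 / 12 / 11% | 0.5-0.9% | 4-5% |

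Most differences are between a winner and no winner. The background rate depends on the set-up. If each simulated patient carries an outcome for both arms, the item change gives 19-27% at 10% v 25%, but a new randomisation alone gives about 18% (4,000 runs).

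**4. If the worst-item rate is not 10%.** With the same 15-point effect, a placebo rate of 20% or 30% on the worst item lowers Pr(active selected) from 0.81 to 0.75 or 0.71. Criterion 3.1.3 selects patients on the worst item (score of at least 6), so equal rates cannot be taken for granted. The size of any difference is unknown. Baseline is measured again after registration, which may absorb part of any regression to the mean.

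**The case against.** The strongest reply is that this is stale wording with little behind it. Section 16 states the endpoint three times and Section 16.1 says that this trial's results will be shadowed, so an analyst working from Section 16 would use the usual item. Section 16.1 also says the concept first proposed a Bayes design, so Appendix X may be carried-over text. The shadow is a feasibility exercise on completed data: it assigns no patient, stops no arm and does not touch the Fisher test. Both items are collected, so the exercise can be rerun on either. The Appendix X table is a generic grid with no item-specific input.

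Most of this stands, and it is why the point is low in severity. It does not remove the contradiction, because Appendix X is where the shadow method is specified.

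Four stronger readings are tempting and are not supported:

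- *The plan deliberately compares two designs on two endpoints.* The documents do not say so. The mixing arises only if Appendix X is followed over Section 16.
- *The question about the Bayes design could not be answered.* It could, by rerunning the shadow on the usual item.
- *The item would often produce a different winner.* At 10% v 25%, opposite winners occur in about 1-2% of runs. A Fisher-only comparison of the two items at 100 per arm disagrees on significance in 20-29% of simulated trials at 10% v 25%, but in only about 5% at 10% v 10% and roughly 7-11% at 10% v 30%. That comparison does not run the Bayes rules, and it never gave significance in opposite directions.
- *The repeated word in Section 16.4.2 proves that worst was changed to usual in Section 16 and missed in the appendix.* It is consistent with that history but does not prove it.

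**Conclusion.** The contradiction holds on the text. Its consequence is conditional: if Appendix X is followed as written, the item is changed along with the design.

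The 20-26% rests on the assumed correlations of 0.6 to 0.9, equal 10% v 25% rates on both items, and a two-arm simplification of a three-arm procedure. Not all of it is due to the item, since a new randomisation sequence on the same item changes the result in 7-8% of runs, or about 18% under the alternative set-up. The figure shows that the choice of item can matter to the shadow result; it does not predict this trial.

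The primary Fisher test, the sample size, the monitoring rules and the conduct of the trial are unaffected. This is a low-severity correction to a planned exploratory analysis.

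**What to change.** 1. In Appendix X, replace the worst-fatigue item with the usual-fatigue item in the endpoint definition, so that it agrees with Sections 16.1, 16.3 and 16.5.
2. In Section 16.4.2, make the list of other fatigue items read worst and now. Usual is the primary item and does not belong among the others, and the worst item, on which eligibility is set, would then be named as a secondary measure.

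The cost is a few words. The BFI, which contains both items, is already collected at baseline and at weeks 4 and 8 (Section 4.0), so no new data are needed. The 10% and 25% rates, the 100 patients per arm and the Appendix X table stay as they are. The correction should be recorded before the shadow analysis is run.
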